5.5.8. Visit Windows

The visit windows for the study are as defined in the protocol. The by-visit analyses will be based on nominal scheduled visits without using the unscheduled visits. Since the evaluation of study drug is for chronic use and using an endpoint that changes over a long term, delayed visits or visits occurring outside of the specified window are likely to have a minimal impact on analyses.

5.6. Multiple Comparisons and Multiplicity

The primary efficacy endpoint, key and other secondary efficacy endpoints will be tested sequentially in the order specified in Section 2 to account for multiplicity and preserve overall Type I error. Each test will be at a type I error level ≤ 0.05 , two-sided to preserve the overall Type I error (first test of primary efficacy is conducted at 0.05). As soon as a given test yields a p-value > 0.05 , all subsequent tests following it will be considered nominal p-values.

No adjustments will be made for multiple comparisons in testing other exploratory efficacy endpoints.

5.7. Analysis by Region and Pooling of Countries with Low Number of Participants

Analyses will be adjusted for region (North America and Europe) as a covariate. Since every country had 9 or more participants, no pooling of subjects is planned for any analyses conducted by country unless otherwise specified. No analyses by center are planned. However, if these are required to be conducted by regulatory authorities, centers with too few participants will be pooled.

5.8. Missing Data and Unscheduled Visits

5.8.1. Missing Efficacy Endpoints

Efficacy variables will be handled using the estimand framework detailed in Section 7.1.

5.8.1.1. Missing Baseline Value

Missing Baseline values for efficacy endpoints will not be imputed for analysis based on observed data since there are only a few participants (<5) missing any baseline efficacy endpoints.

Missing Baseline covariate variables used as covariates in analysis models such as Mixed Model Repeated Measures (MMRM) will be replaced using mean imputation. Since the participants are randomized at Baseline to help ensure balance between treatment groups, the missing values will be imputed by the mean values, as calculated from a regression model with pooled non-missing values for the Baseline variable from both treatment groups as dependent variable adjusting for the randomization stratification factors. For binary variables, coded 0 or 1 for example, the imputed mean will be rounded up to 1 or down to 0, whichever is nearest.

5.8.1.2. Missing Post-baseline Efficacy Data

Missing data will be handled using statistical methods based on National Research Council's *The Prevention and Treatment of Missing Data in Clinical Trials*.

For an analysis with the MMRM model that uses restricted maximum likelihood for estimation, no imputation will be used, and the model will include all observed data to estimate the treatment effect of change from Baseline to Week 65 in UHDRS-TFC, under the assumption of missing at random (MAR).

To evaluate the possible impact of missing values on the primary and select secondary efficacy analyses, the method of multiple imputations (MI) will be used to evaluate the robustness of data assumptions, imputing data under MAR and missing not at random (MNAR), using different assumptions about the treatment effect for the unobserved data. Additional details are provided below.

Missing data are considered monotone if after a certain time point the data are no longer available. This happens when a participant discontinues from the study and there are no assessments after the last visit when the participant was assessed. It is expected that the great majority of missing data will have a monotone pattern. Different assumptions, such as MAR and MNAR, will be made on the monotone missing pattern to show the robustness of estimates. There is also some small amount of non-monotone missing data when there are intermediate time

points of missing data, such as due to missed visits, which will be assumed to follow MAR assumptions. Methods as described below will be adopted to estimate for both non-monotone and monotone missing data patterns.

- Imputation for non-monotone missing data pattern will be based on the initial imputation using Markov Chain Monte Carlo (MCMC) by generating 100 datasets with only monotone missing data. For participants with intermittent missing values, a monotone missingness pattern will be generated in each of the 100 datasets. This imputation step is based on the MAR assumption. In both methods below (under MAR or MNAR) the MI step will generate 100 complete datasets with no missing values.

MAR and MNAR imputation vary at the handling of monotone missing data pattern.

- Under the assumptions of MAR that missingness depends on the observed values and can be predicted based on a participant's observed data, the missing value will be imputed using monotone regression model. The imputation model will include Baseline and all post-baseline values for the efficacy endpoint to be imputed, treatment, randomization strata, and region. Multiple imputations will be performed to assign the response variable at consecutive study visits in a sequential manner for the monotone missing data pattern.
- Under the assumptions of MNAR that missingness depends on unobserved values and cannot be predicted solely based on a participant's observed data, the missing value will be imputed using a pattern-mixture model (PMM). In the PMM, the distribution of a response is modeled as the mixture of a distribution of the observed responses and a distribution of the missing responses. As the missing values for participants in the pridopidine group may imply these participants no longer receive the treatment, it is then reasonable to assume that the conditional distribution of the missing values, given observed data, is similar to that in the placebo group, and impute the missing values in pridopidine group based on the conditional distribution from the placebo group.

This will be realized by PMM with control-based pattern imputation, a variant of the copy reference method (Little and Wang, 1996; Ratitch and O'Kelly, 2013). In this imputation approach, the model for missing observations is constructed from the observed data in the placebo group only, and then used as the imputation model for missing values in pridopidine and placebo groups. Following the chain-based imputations, multiply imputed datasets will be analyzed using the same MMRM as for primary analysis (Section 7.2).

At the last step, the estimates from all imputed datasets will be combined using Rubin's rule for an overall inference. SAS Procedures, MI, MIXED and MIANALYZE will be used for above steps.

5.8.1.3. Missing Item Scores in Derivation of Total Scale Score

5.8.1.3.1. Missing items on Unified Huntington's Disease Rating Scale – Total Functional Capacity(UHDRS-TFC)

A TFC is considered valid if all 5 domains are scored. If any item is left blank the TFC is considered missing.

5.8.1.3.2. Missing items on Unified Huntington's Disease Rating Scale – Total Motor Score (UHDRS-TMS)

If at least 16 out of the 31 items on the TMS are scored, the total TMS score will be computed the following way. The observed sum of score from the available items is divided by the total number of the available items, and then multiplied by 31 to get the overall TMS score. For example, if 20 items were completed with a score of 60, then TMS Score will be $(60/20) \times 31$, or 93.

If there are more than 5% of all TMS assessments which required imputation per the above rule, then a sensitivity analysis will be performed excluding those TMS scores that required imputation of partial items.

5.8.1.3.3. Missing items on HDQoL and Other Subscale Scores

A similar approach as above will be used by which the score on missing items will be imputed using the average of the scores on items that were completed.

5.8.2. Missing Start and Stop Dates for Prior / Concomitant Medication, Medical History for HD Diagnosis and Adverse Events

Missing start or stop dates for prior/concomitant medications

The following rules will be used in this study to define concomitant for medications with completely missing start or stop dates:

- If both start and stop dates of a medication or therapy are completely missing, this medication or therapy will be considered both prior and concomitant.
- If the start date of a medication or therapy is completely missing and the stop date is on or after the date of the first dose date of study treatment, that medication or therapy will be considered both prior and concomitant.
- If the stop date of a medication or therapy is completely missing and the start date is after the first dose of study drug, that medication or therapy will be considered concomitant.

For medications with partial missing dates, following imputation rules will be used:

- For partial start dates, missing month will be imputed with January and missing day will be imputed with first day of the month.
- For partial stop dates, missing month will be imputed with December and missing day will be imputed with the last day of the month.

If a medication has a missing or partial missing start/end date or time and cannot be determined whether the medication is taken before first dose or concomitantly, it will be classified as both prior and concomitant.

Missing dates for Medical History for HD Diagnosis

In order to determine onset of symptoms data are collected for who first noticed symptoms (Participant, Family, Rater) and what the symptoms were (Motor, Cognitive, Psychiatric or Other). Since dates are not always exactly known a mid-point of interval rule will be used. If date is missing it will be assumed to be the 15th of the month, if month is missing it will assume

to be June (6th month). To compute the years since onset of HD symptoms the earliest of these dates will be used and subtracted from the screening date.

Missing start date for AEs

The treatment-emergent adverse events (TEAEs) are determined by the start date of the AEs. If the start date of an AE is completely missing, then the AE is considered as treatment-emergent. If the start date of an AE is partially missing, the AE start date will be imputed as follows:

- Missing day – Impute the 1st of the month. If the month and year of AE is same as month and year of the first dose of study drug, then impute first dose date, ensuring the AE is a TEAE.
- Missing day and month – Impute 1st January. If the year is the same as the year of the first dose date, then impute the first dose date, ensuring the AE is a TEAE.
- If AE start date is completely missing it will be set to the treatment start date.

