8.3.1. Time Period and Frequency for Collecting AE and SAE Information

All AE and SAEs will be collected from the signing of the ICF until the last Follow-up visit at the timepoints specified in the SoA ([Table 2 – Main Study](#), and [Table 3 – OLE](#)). Assessment should be done through on-site clinic visits, safety TCs, and virtual visits (via telephone).

An event that emerged during or after treatment or worsened relative to the pretreatment state will be recorded as a treatment-emergent adverse event (TEAE).

All SAEs will be recorded and reported to the Sponsor or designee immediately upon any site study staff becoming aware and under no circumstance should this exceed 24 hours, as indicated in Appendix 3 (Section 10.3). The Investigator will submit any updated SAE data to the Sponsor within 24 hours of it being available.

Investigators are not obligated to actively seek AE or SAE after conclusion of the study participation. However, if the Investigator learns of any SAE, including death, at any time after a participant has been discharged from the hospital, and he/she considers the event to be reasonably related to the study drug or study participation, the Investigator must promptly notify the Sponsor.

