8.4. Adverse Events

All AEs will be coded using MedDRA Version 23.0 (or a later version if updated during the study).

For statistical analysis, a TEAE is defined as an AE that occurs for the first time or worsens (as captured on the eCRF) on or after initiation of treatment in the corresponding analysis period (Main Study or OLE Treatment Period) EoS. Due to the short half-life of Pridopidine (10-12 hrs) AEs that started more than 14 days after end of treatment are not considered TEAEs.

The terms AEs and TEAEs are used interchangeably in this SAP and unless otherwise specified refer to TEAEs.

An overall summary will be presented by treatment groups that includes the number and percentage of participants who experienced at least one TEAE for the following categories: All TEAEs, serious TEAEs, TEAEs leading to study discontinuation, TEAEs leading to death, TEAEs based on maximal Severity, TEAEs leading to study drug withdrawal anytime during the study, TEAEs leading to study drug withdrawal during titration. When appropriate, a total column may appear as the last column.

Summaries will be presented for all TEAEs by SOC and PT for the following categories of TEAEs:

- TEAEs, severe TEAEs, Treatment-related TEAEs, Serious TEAEs (see below for more details), TEAEs potentially related to QT prolongation, (e.g., palpitations, dizziness, syncope, cardiac arrhythmias, and sudden death), TEAEs related to abuse potential (See Appendix 12.2 for the AE terms), TEAEs causing discontinuation from the study.

The above summaries will include the number of events as well as number and percentage of participants experiencing at least one TEAE in each SOC and PT. To count the number of participants with any TEAEs, a participant who experiences multiple TEAEs within the same SOC will be counted only once for that SOC (if the TEAEs are coded to the same PT). A participant who experiences multiple TEAEs coded to the same PT within the same SOC will be counted only once for that PT. The number and percentage of participants experiencing any TEAE will also be provided. All percentages will use the number of participants in the SP within that treatment group as the denominator. In the summaries SOCs will be sorted in descending order based on number of participants in Total column; PT within SOC will be sorted by descending number of participants in Total column.

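### SAP 5.8.2 dates some AEs with an incomplete start date to first dose without checking the stop date, so an AE that ended before dosing can be counted as treatment-emergent

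*SAP*

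**What the plan says.** SAP 5.8.2, under the heading on missing AE start dates, makes the start date the sole criterion: "The treatment-emergent adverse events (TEAEs) are determined by the start date of the AEs". It then gives these rules.

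- Start completely missing: "If the start date of an AE is completely missing, then the AE is considered as treatment-emergent". For the date itself, "If AE start date is completely missing it will be set to the treatment start date".
- Day missing: the 1st of the month is used, unless the month and year are the "same as month and year of the first dose of study drug, then impute first dose date, ensuring the AE is a TEAE".
- Day and month missing: 1 January is used, unless the year is that of first dose, in which case the first dose date is used, again so that the AE counts as treatment-emergent.

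SAP 8.4 gives the definition these rules serve: "a TEAE is defined as an AE that occurs for the first time or worsens" on or after the start of treatment in the analysis period. Its only other date limit excludes AEs starting more than 14 days after the end of treatment.

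On collection, Protocol 8.3.1 states: "All AE and SAEs will be collected from the signing of the ICF". SAP 8.1 says collection runs from the Screening visit.

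**The concern.** Dating an AE to first dose when its timing is unknown is ordinary conservative practice. The difficulty arises when the timing is known. If the recorded stop date falls before first dose, the event cannot have begun on or after first dose, whatever its start date was. Under the three patterns above, the rule still assigns the first dose date and counts the event as a TEAE. The record then has a start later than its stop and fails the SAP's own definition.

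At stake is the correctness of individual entries in the TEAE tables and listings. One extra event matters most where counts are low, such as a rare preferred term.

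**Working it through.** No figure in the plan needs reproducing. The check applies the rule literally, then compares it with the medication rule in the same section.

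**Inputs.** The imputation rules are from SAP 5.8.2 and the TEAE definition from SAP 8.4. The screening length is from Protocol 4.1: up to 6 weeks (42 days), or 3 weeks (21 days) when no genetic test or washout is needed. The number randomized (499) is from the SAP version history.

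**Step 1: invented test case.** First dose is 20 March 2021 and the recorded AE stop is 10 March 2021.

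| Recorded start | Imputed start | TEAE under the rule? | Imputed start minus stop |
|---|---|---|---|
| completely missing | 20 Mar 2021 | yes | +10 days |
| ??-Mar-2021 | 20 Mar 2021 | yes | +10 days |
| ??-??-2021 | 20 Mar 2021 | yes | +10 days |
| ??-Feb-2021 | 1 Feb 2021 | no | −37 days |
| ??-??-2020 | 1 Jan 2020 | no | −434 days |

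The first three rows are wrong and the last two are right.

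**Step 2: how often a screening-onset AE falls under the rule, given an incomplete start date.** Assume first dose is equally likely on each day of 2021 and onset is equally likely on each of the W days before it. This gives 365 × W pairs: 7,665 for W = 21 and 15,330 for W = 42.

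- Start completely missing: 100% are dated to first dose.
- Day and month missing: all pairs except those crossing into the previous year. Those number W(W+1)/2, which is 231 for W = 21 and 903 for W = 42. The shares are 1 − 231/7,665 = 97% and 1 − 903/15,330 = 94%.
- Day only missing: pairs in the same calendar month number 4,893 for W = 21 and 5,373 for W = 42. The shares are 4,893/7,665 = 64% and 5,373/15,330 = 35%.

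These are shares of AEs that already have that missing pattern. Only those that also have a recorded pre-dose stop are certainly misclassified.

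**Step 3: effect of one event.** With about 499/2 = 249.5 participants per arm, one additional participant with an event adds 1/249.5 = 0.4 percentage points. If five such participants are assumed across both arms, the pooled shift is 5/499 = 1.0 point. If there are none, it is zero.

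**Step 4: the medication rule.** For a medication whose start "is completely missing and the stop date is on or after the date of the first dose date", SAP 5.8.2 assigns both the prior and the concomitant category. The stop date is therefore a condition there, and a pre-dose stop does not make the medication concomitant under that bullet. The AE bullets have no equivalent.

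**Step 5: a correction elsewhere?** The 14-day limit in SAP 8.4 acts only after treatment ends. SAP 5.8.3 says generally that missing safety data are not imputed. The specific AE rule in 5.8.2 still stands, and its treatment-emergent status for a completely missing start is assigned outright. Neither section supplies a stop-date check.

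**The case against.** The strongest reply is that the rule is deliberately conservative and the case is rare. AE inquiry takes place at every contact from Screening. AE information is due in the eCRF within 24 hours of site awareness (Protocol 10.3.4), sources are verified (Protocol 10.1.6), and consistency checks are run (SAP 5.3). A known stop within a six-week window with an unknown start is the kind of record that would be queried. This stands as an argument about frequency, and the number of affected events may well be zero. It does not rescue the wording. Conservatism resolves an unknown, and here the recorded stop date settles the question.

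Several stronger readings are tempting, and the documents do not support them.

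- A reader might infer that every missing or partial start date goes to first dose. Partial dates do so only when the known month and year, or the known year, match first dose.
- A reader might infer that the treatment-related TEAE table is distorted. Under Protocol 10.3.4, relatedness rests on causation by, or a temporal relationship to, the study drug. An event that ended before any dose should be rated not related.
- A serious event resolved in screening with its start still incomplete at database lock is possible but remote, given 24-hour SAE reporting.
- A reader might expect distorted durations or a compromised test between arms. SAP 8.4 plans neither an AE duration analysis nor a between-arm AE test. The later-than-stop start would show, at most, as an odd derived date in a listing.

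**Conclusion.** The point holds as a narrow drafting error. For an AE with a recorded stop before first dose, and a start that is completely missing or partial and matching first dose as described, the stated rule gives a classification that SAP 8.4 contradicts.

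The practical size is small. The documents give no count, and zero to a few is my assumption. The error runs in one direction, over-counting TEAEs. It should be similar in both arms because the events precede dosing and the rule is the same for each. The primary endpoint, the testing hierarchy and all other efficacy results are untouched. The change is worth making because it is nearly free, but nothing in the trial's conclusions depends on it.

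**What to change.** Add at the head of the AE rules in SAP 5.8.2:

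> If the AE stop date, or its latest possible value when partial, is before first dose, the AE is not treatment-emergent and its start date is not imputed beyond the stop date; otherwise the rules below apply.

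In the test case, the imputed start would then be no later than 10 March 2021 and the AE would not be a TEAE. AEs whose stop date is missing, or falls on or after first dose, keep the present conservative handling.

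The cost is one sentence and one condition in the derivation program. SAP section 5 provides for an addendum for changes before database lock and unblinding. After unblinding, the same section sends the change to the clinical study report as a change to planned analyses. A short cross-reference in SAP 5.8.3, noting that AE dates are the exception to its no-imputation statement, would remove the remaining ambiguity.

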5.8.3. Missing Demographics, Baseline Characteristics, Exposure or Safety Data

Only observed demographics, baseline characteristics, exposure, and safety data will be presented. No imputations will be performed. For efficacy analysis if a baseline covariate is missing it will be imputed as described in Section [5.8.1](#).

5.8.4. Unscheduled Visits

Summaries of efficacy data will only use data collected at scheduled visits, unless data is not available at the required post-baseline visit and the only available data is from an unscheduled visit close to the scheduled visit within an acceptable time window. If the unscheduled visit efficacy assessment is not within the acceptable window it will be ignored from the efficacy analyses, but will be identified in listings.

For descriptive statistics on continuous safety variables only data collected at scheduled visits will be used. For summary of abnormalities or shift tables all available data from scheduled and unscheduled visits will be used. Abnormality tables and shift tables will display the worst value across all visits, the last available non-missing value, and the values by scheduled visits. For shift tables, if there is more than one abnormality in the time period specified, the worst value will be used. When summarizing “worst” values if the participant had both a low and high value they will be included in both rows.

